### **6.3 PATIENT SETS ANALYSED**

- **Treated set:**  
This patient set includes all patients who were dispensed study medication and were documented to have taken at least one dose of investigational treatment.
- **PK set:**  
This patient set includes all patients in the treated set with at least one evaluable PK parameter in the treatment period. The patients with important PVs related to PK will be excluded from PK set.

### **6.4 SUBGROUPS**

No subgroup is defined in this trial.

### **6.5 POOLING OF CENTRES**

This section is not applicable, because the study was performed in only one centre.

### **6.6 HANDLING OF MISSING DATA AND OUTLIERS**

Missing safety data will not be imputed with the exception of missing adverse event (AE) dates which will be imputed according to Boehringer Ingelheim (BI) standards (see “Handling of missing and incomplete AE dates”). [\(2\)](#)

Missing data and outliers of PK data are handled according to 001-MCS-36-472, RD-01 [\(1\)](#) [\(6\)](#).

### **6.7 BASELINE, TIME WINDOWS AND CALCULATED VISITS**

The definition of baseline values is described in the CTP, Section 7.1 ‘STATISTICAL DESIGN – MODEL’.

## **7. PLANNED ANALYSIS**

Non-pharmacokinetic variables:

For End-Of-Text tables, the set of summary statistics is: N / Mean / SD / Minimum / Median / Maximum.

Tabulations of frequencies for categorical data will include all possible categories and will display the number of observations in a category as well as the percentage (%) (unless otherwise specified, all patients in the respective patient set whether they have non-missing values or not). Percentages will be rounded to one decimal place. The category missing will be displayed only if there are actually missing values.

Pharmacokinetic variables:

For all pharmacokinetic tables, the set of descriptive statistics is: N (number of subjects with nonmissing values) / Mean / geometric mean (gMean) / SD / coefficient of variation (CV) / geometric coefficient of variation (gCV) / Min / 10th percentile (P10) / Q1 (lower quartile) / Median / Q3 (upper quartile) / 90th percentile (P90) / Max.

### **7.1 DEMOGRAPHIC AND OTHER BASELINE CHARACTERISTICS**

Only descriptive statistics are planned for this section of the report. COPD background characteristics will be listed only.

### **7.2 CONCOMITANT DISEASES AND MEDICATION**

Concomitant diseases will be coded similarly as the AEs based on the most recent version of Medical Dictionary for Regulatory Activities (MedDRA). Concomitant medications will be coded according to the most recent version of World Health Organization Drug Dictionary.

Only descriptive statistics are planned for this section of the report.

### **7.3 TREATMENT COMPLIANCE**

Only descriptive statistics are planned for this section of the report.

### **7.4 PRIMARY ENDPOINTS**

No efficacy endpoint is defined in this trial.

Primary pharmacokinetic endpoints will be analysed as described in [Sections 7.9](#).

### **7.5 SECONDARY ENDPOINTS**

See [Section 7.8](#) for safety analyses which are the secondary objectives of this trial.

## 7.7 EXTENT OF EXPOSURE

Only descriptive statistics are planned for this section of the report.

## 7.8 SAFETY ANALYSIS

All safety analyses will be performed on the treated set.

### 7.8.1 Adverse events

The analyses of AEs will be descriptive in nature and will be based on BI standards (see 'Handling and summarisation of adverse event data for clinical trial reports and integrated summaries') (3). All analyses of AEs will be based on the number of patients with AEs (not the number of AEs).

For analysis of AE attributes such as duration, severity, etc. multiple AE occurrence data on the Case Report Form, will be collapsed into AE episodes provided that all of the following applies:

- The same MedDRA lowest level term was reported for the occurrences
- The occurrences were time-overlapping or time-adjacent (time-adjacency of 2 occurrences is given if the second occurrence started on the same day or on the day after the end of the first occurrence)
- Treatment did not change between the onset of the occurrences OR treatment changed between the onset of the occurrences, but no deterioration was observed for the later occurrence

For further details on summarization of AE data, please refer the BI guidelines. (2), (3).

The analysis of AEs will be based on the concept of treatment emergent AEs. That means that all AEs occurring between first drug intake till 21 days after last drug intake will be assigned to the treatment. All AEs occurring before first drug intake will be assigned to 'screening' and all AEs occurring after last drug intake + 21 days will be assigned to 'follow-up' (for listings only).

According to ICH E3 (4), AEs classified as 'other significant' needs to be reported and will include those non-serious and non-significant AEs with

- (i) 'action taken = discontinuation' or 'action taken = reduced', or
- (ii) marked haematological and other lab abnormalities or lead to significant concomitant therapy as identified by the Clinical Monitor/Investigator at a Medical Quality Review Meeting (MQRM).

An overall summary of AEs will be presented.

The frequency of patients with AEs will be summarised by treatment, primary system organ class (SOC) and preferred term (PT). Separate tables will be provided for patients with other significant AEs according to ICH E3 (4), for patients with AEs leading to death, for patients with AEs leading to treatment discontinuation, for patients with AEs of special interest, for patients with serious AEs, for patients with related serious AEs, and for patients with drug-related AEs. The frequency of patients with AEs will also be summarised by intensity, treatment, primary SOC and PT.

The SOCs will be sorted according to the standard sort order specified by European Medicines Agency. PTs will be sorted by frequency (within SOC).

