5.1.2 Secondary Endpoints

The number (%) of subjects with drug related Adverse Events will be determined as secondary endpoint to assess safety and tolerability of tiotropium + olodaterol fixed-dose combination (5 µg/ 5 µg).

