7.3.4 Safety analyses

Adverse events will be coded using the Medical Dictionary for Regulatory Activities (MedDRA) coding dictionary. Standard BI summary tables and listings will be produced. All adverse events with an onset between start of treatment and end of the residual effect period (REP), a period of 21 days after the last dose of trial medication, will be assigned to the treatment period for evaluation.

All treated patients will be included in the safety analysis. In general, safety analyses will be descriptive in nature and will be based on BI standards. No hypothesis testing is planned.

Statistical analysis and reporting of adverse events will concentrate on treatment-emergent adverse events. To this end, all adverse events occurring between start of treatment and end of the residual effect period will be considered 'treatment-emergent'. Adverse events that start before first drug intake and deteriorate under treatment will also be considered as 'treatment-emergent'.

Frequency, severity, and causal relationship of adverse events will be tabulated by system organ class and preferred term after coding according to the current version of the Medical Dictionary for Drug Regulatory Activities (MedDRA).

Laboratory data will be analysed both quantitatively as well as qualitatively. The latter will be done via comparison of laboratory data to their reference ranges. Values outside the reference range as well as values defined as clinically relevant will be highlighted in the listings.

Vital signs, physical examinations, or other safety-relevant data observed at screening, baseline, during the course of the trial and at the end-of-trial evaluation will be assessed with regard to possible changes compared to findings before start of treatment.

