#### **4. CHANGES IN THE PLANNED ANALYSIS OF THE STUDY**

There has been no change in the planned analyses from the statistical methods described in the CTP.

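### SAP 7.8.1 assigns all pre-dose AEs to screening and omits the protocol's exception for those that worsen on treatment, so the secondary endpoint can be under-counted

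*SAP*

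**What the plan says.** Protocol 7.3.4 gives two routes to treatment-emergent status. The first is by onset: "All adverse events with an onset between start of treatment and end of the residual effect period (REP"), where that period lasts 21 days after the last dose, are assigned to the treatment period. The second is by deterioration: "Adverse events that start before first drug intake and deteriorate under treatment will also be considered as" treatment-emergent.

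SAP 7.8.1 says it works with the treatment-emergent concept, but spells it out by date only: "all AEs occurring between first drug intake till 21 days after last drug intake will be assigned to the treatment". It then adds: "All AEs occurring before first drug intake will be assigned to" screening. SAP 6.1 likewise defines the on-treatment period by dates alone.

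SAP 7.8.1 mentions deterioration in one place, the rule for merging several recorded occurrences into one episode. Occurrences that straddle a treatment change may be merged only where "treatment changed between the onset of the occurrences, but no deterioration was observed for the later occurrence".

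SAP section 4 states: "There has been no change in the planned analyses from the statistical methods described in the CTP".

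The endpoint concerned is in Protocol 5.1.2: "The number (%) of subjects with drug related Adverse Events will be determined as secondary endpoint". SAP 7.5 refers it to the safety section, where 7.8.1 lists a table of patients with drug-related AEs.

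**The concern.** The two assignment rules give different answers for one class of event: an AE already present before the first dose that gets worse on the drug. The protocol counts it as treatment-emergent. The SAP, read plainly, sends it to screening. Because the SAP declares no change, a programmer working from it would have no reason to look for the missing rule.

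Such events can exist in the data. Protocol 5.3.7 collects AEs from informed consent. Visit 1 may fall up to 28 days after consent, and screening then lasts 2 to 4 weeks. If one of these events worsens on treatment and is judged drug-related, it belongs in the secondary endpoint under the protocol but may be absent from the table that reports it. The other AE tables in SAP 7.8.1 (serious, special interest, by intensity) rest on the same assignment. In a trial of this size, one patient visibly changes the percentage.

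**Working it through.** **Comparing the rules.**

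| AE | Protocol 7.3.4 | SAP 7.8.1 |
|---|---|---|
| Starts between first dose and last dose + 21 days | Treatment-emergent | Treatment |
| Starts before first dose, does not worsen | Not treatment-emergent | Screening |
| Starts before first dose, worsens under treatment | Treatment-emergent | Screening, no exception stated |

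The rules differ only in the third row, and there the SAP can only remove events relative to the protocol.

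**How the third row plays out in the data.** It depends on how the worsening is recorded.

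1. *New occurrence with an on-treatment onset.* If the move from screening to dosing counts as a treatment change, the merging rule keeps a deteriorated later occurrence separate. Its onset is on treatment, so it is assigned to treatment and nothing is lost.
2. *Same record, pre-dose onset kept.* The merging rule needs more than one recorded occurrence, so it does not apply. The event goes to screening and is absent from the drug-related AE table.

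Protocol 5.3.7 asks for worsening of the underlying disease or of other pre-existing conditions to be recorded as an AE. That points towards the first case for some events. It does not say that an AE already open from screening is to be closed and re-entered with a new onset date, and the SAP does not say so either.

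**When the endpoint changes.** A patient is lost from the numerator only if all of these hold: an AE starts before dosing; it deteriorates on treatment; it is judged drug-related; it remains on one record; and the patient has no other drug-related AE on treatment.

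**Size.** Inputs are from Protocol 7.7: 12 evaluable patients and 25% dropout.

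- Planned number: 12 / (1 − 0.25) = 16, which matches the protocol.
- Weight of one patient: 1/16 = 6.25 percentage points. Two patients: 2/16 = 12.5. Three: 3/16 = 18.75.
- If only 12 were treated: 1/12 = 8.33 points.

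**Chance of at least one lost patient.** The documents give no AE rates, so this is illustration only. Let q be an assumed probability that a given patient meets all the conditions above. With 16 independent patients the chance is 1 − (1 − q)^16:

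- q = 1%: 14.9%
- q = 2%: 27.6%
- q = 5%: 56.0%
- q = 10%: 81.5%

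Nothing in the documents indicates which q is realistic.

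**The case against.** The strongest case for the SAP is that it means to apply the protocol definition. It invokes the treatment-emergent concept, says in its introduction that it is based on section 7 of the protocol, and declares no change. Its merging rule respects deterioration at record level. It also refers to company standards for AE handling, which are not available here and may contain the rule. Finally, its word is occurring, not onset.

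Much of this stands as evidence of intent. The merging rule does save events entered as a second occurrence, and the instruction in Protocol 5.3.7 makes that entry likely in some cases. It does not remove the conflict. The assignment sentence covers all pre-dose AEs, and a standard that cannot be seen should not be assumed to override it. If that standard does include deterioration, the SAP text contradicts its own reference and still needs correcting. Onset is the natural reading of occurring. If it meant ongoing, an AE spanning the first dose would fall in both categories, which also needs resolving.

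Two stronger readings are tempting, and the documents support neither:

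- A reader might infer that the SAP rule biases the endpoint downwards in any event. It does not: the loss requires every condition listed in the working, including a data-entry practice that neither document describes.
- A reader might infer that withdrawing long-acting bronchodilators during screening makes such events likely. Withdrawal makes pre-dose AEs plausible, but only worsening on treatment matters. Dosing supplies two long-acting bronchodilators, and Protocol 2.3 expects bronchodilating benefit, so withdrawal symptoms would more plausibly improve.

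**Conclusion.** The conflict between Protocol 7.3.4 and SAP 7.8.1 is real on the plain wording, and SAP section 4 does not disclose it. It reaches the only secondary endpoint, which can be under-counted relative to the protocol definition when a worsening screening AE stays on its original record.

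Each affected patient is 6.25 percentage points at the planned 16. That is the weight of one patient and does not estimate the error; the frequency is unknown. The 8.33-point figure should not be taken as the general case. The target of 12 is defined in Protocol 3.3.1 by available PK samples, whereas safety uses the treated set, so the figure applies only if just 12 patients are treated.

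The conclusion assumes that occurring means onset and that no unseen company standard replaces the stated rule. No hypothesis is tested, so type I error, power and sample size are unaffected. The SAP should be corrected; the point does not call the design into question.

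**What to change.** 1. In SAP 7.8.1, add the protocol's own rule as an exception to the screening assignment: "Adverse events that start before first drug intake and deteriorate under treatment will also be considered as" treatment-emergent, and are assigned to treatment. The protocol's term is enough. Adding further criteria such as a change in seriousness, or a worsening date that the documents do not show being collected, would go beyond the protocol and would itself need declaring in SAP section 4.
2. Programme all AE tables, including the drug-related AE table, on that definition.
3. State that a screening AE that worsens after the first dose is entered as a new occurrence with its own onset. Without this, deterioration may not be identifiable from a single record.

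The cost is one or two sentences and one derivation step. If the sponsor prefers the date-only rule, SAP section 4 should declare it as a change from the protocol.

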### **7.8.2 Laboratory data**

The analyses of laboratory data will be descriptive in nature and will be based on BI standards (5).

### **7.8.3 Vital signs**

Only descriptive statistics are planned for this section of the report.

### **7.8.4 ECG**

Not applicable as ECG measurement data are not collected in this study.

### **7.8.5 Others**

Not applicable since no other endpoint was planned.

## **7.9 PK ANALYSIS**

The analysis of standard PK parameters will be performed according to 001-MCS-36-472 RD-01 (6), and also as described in CTP Section 7.3.

## **9. ADDITIONAL SECTIONS**

Not applicable as no additional information is needed.

## 10. HISTORY TABLE

Table 10: 1 History table

Version	Date (DD-Mmm-YY)	Author	Sections changed	Brief description of change
Initial	01-Mar-2017		None	This is the initial TSAP with necessary information for trial conduct
Final	30-Jun-2017		None	This is the final TSAP
